7a. Do you have any questions (*RESPOND TO ANY QUESTIONS ASKED*).

Thank so much you for your time (*END CALL*).

8. Among Participants who identified one or more needs, randomize to one of three study arms.

9. Among participants randomized to Arm 1 (Screening): Thank you for completing Part One of the study. You are eligible for Part Two of the study and have been randomized to Group A. This means that in 8 weeks, I will recontact you to ask a few more questions about your needs. Do you have any questions? (*RESPOND TO ANY QUESTIONS ASKED*) (*MENTION GIFT CARD AND VERIFY MAILING ADDRESS**.) Thank you for your time.

**(CIRB Note: local sites will explain their payment process, which differs from the prime site)*

10. Among participants randomized to Arm 2 (Awareness): Thank you for completing Part One of the study. You are eligible for Part Two of the study and have been randomized to Group B. I would like to provide you with some written material about programs and agencies that might be able to help you with the needs you identified. I will mail you this material within the next two business days. If you like, I can also email the material to you right now and we can review it together over the phone. Would you like to do that?

If Yes to email: Great, I can email that to you right now. (CONFIRM/ASK FOR PARTICIPANT'S EMAIL ADDRESS AND SEND ENCRYPTED EMAIL.)

If No to email: No problem. You can look for a written list of resources in the mail in the next several days. The information will include my phone number in case you have any questions about the information once you receive it.

10a. I will also be mailing you a \$15 gift card* to thank you for your time. And in 8 weeks, I will recontact you to ask a few more questions about your needs. Do you have any questions? (RESPOND TO ANY QUESTIONS ASKED) (VERIFY MAILING ADDRESS FOR GIFT CARD)* Thank you for your time.

[\(CIRB Note: local sites will explain their payment process, which differs from the prime site.\)](#)*

11. **Among participants randomized to Arm 3 (Assistance):** Thank you for completing Part One of the study. You are eligible for Part Two of the study and have been randomized to Group C. I would like to provide you with some written material about programs and agencies that might be able to help you with the needs you identified. I will mail you this material within the next two business days. If you like, I can also email the material to you right now and we can review it together over the phone. Would you like to do that?

If Yes to email: Great, I can email that to you right now. (CONFIRM/ASK FOR PARTICIPANT'S EMAIL ADDRESS AND SEND ENCRYPTED EMAIL.)

If No: to email: No problem. You can look for a written list of resources in the mail in the next several days. The information will include my phone number in case you have any questions about the information once you receive it.

11a. I would also like offer you the assistance of a Social Worker (SW), who can assist you to connect to programs and agencies that might be able to help with the needs you identified. Would you like to receive this assistance?

If No: I encourage you to accept this assistance because it can be helpful. Are you sure you don't want assistance from a SW who can assist you to connect to services?

If does not want SW assistance: (GO TO #11b)

If wants SW assistance: (GO TO NEXT QUESTION)

If Yes: Terrific. The SW on the study team – his/her name is (insert name) -- will call you within two business days. Let me give you the name and number of the social worker so you have it. Do you have a pen and paper? (WAIT FOR PEN AND PAPER AND THEN PROVIDE NAME AND NUMBER)

11b. In 8 weeks, I will recontact you to ask a few more questions about your needs. Do you have any questions? (RESPOND TO ANY QUESTIONS ASKED) (MENTION GIFT CARD AND VERIFY MAILING ADDRESS)* Thank you for your time.

**(CIRB Note: local sites will explain their payment process, which differs from the prime site.)*

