3.0 Objectives

We will compare outcomes among Veterans with or at risk for CVD at three VA sites randomized (at the site-level) to one of three arms: 1) unmet needs screening only, 2) screening + provision of tailored resource sheets to address identified unmet needs, or 3) screening + tailored resource sheet + social worker support. We will quantitatively examine associations of unmet needs with baseline and follow up outcomes, assessing the impact of varying intensity referral approaches. We will also qualitatively examine stakeholder perspectives about the barriers and facilitators to identifying and addressing unmet needs to provide insight into the relative success of each study arm. Specific aims are:

Aim 1: Describe the prevalence and distribution of nine unmet needs (housing, food insecurity, utility insecurity, transportation, legal needs, employment, safety, social isolation, stress), and identify their associations with baseline sociodemographic characteristics, adherence, utilization and clinical outcomes.

Aim 2: Compare the effectiveness of varying intensity referral strategies to address unmet needs on the primary outcome of connection to new resources to address unmet needs, and on secondary outcomes of post-intervention change in unmet needs, adherence, utilization, and clinical outcomes. **H1.** Based on Maslow's model, we hypothesize that referrals (and more so for those enhanced by SW support) will increase the likelihood of patients connecting to new resources to address unmet needs (primary outcome), which may then have positive sequential effects, with reduced unmet needs, increased adherence, decreased urgent care/preventable utilization, and ultimately, improved clinical outcomes.

Aim 3: Identify barriers and facilitators to Veterans' connecting with resources to address unmet needs and getting needs met, and explore potential explanatory factors related to the relative success of each study arm.

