In **Phase Two (Aim 3)**, we will conduct qualitative interviews with a purposeful sample of Veterans (N=60) and representatives of the VA- and community-based programs to which Veterans are referred (N=15). The interviews are designed to understand the conditions that facilitate and impede Veterans’ connection to resources and unmet need reduction, and to identify potential explanatory factors related to the relative success of the interventions. We will follow standard qualitative methods for data collection, coding, and analysis.

Risk to Subjects

We are implementing a non-invasive behavioral intervention by screening and referring Veterans in some study arms to resources to address unmet needs, and in one arm, connecting Veterans with a social worker to support them in connecting to resources. Potential risks are minimal and would primarily involve loss of confidentiality, as follows.

Phase One

- **Quantitative Data (Administrative Databases):** Given that we are using existing data sources, there will be no direct health risks to subjects as a result of the proposed research. The risks associated with the use of these existing data sources would be due to possible breaches of privacy and confidentiality.
- **Quantitative Data (Surveys):** Potential risks may include breaches of privacy and confidentiality. Veterans answering the survey items may also feel inconvenienced and/or uncomfortable answering questions about unmet needs and connection to resources to address unmet needs. Finally, Veterans randomized to the least referral-intense arm (screening-only) could get frustrated with this assignment if they want more assistance with identified needs than this arm offers.

Phase Two

- Qualitative Data (Interviews): For the interviews with Veterans and representatives of organizations providing resources to help Veterans address unmet needs, potential risks may include breaches of privacy and confidentiality, inconvenience, as well as discomfort (in the case of Veterans) answering questions about unmet needs and accessing resources.

Adequacy of Protection from Risk

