Step 3 (phone follow-up to recruit, consent, and screen for eligibility): The research team will provide the final list of site-specific eligible Veterans who did not return an opt-out card to the RA situated at each study site. Guided by a phone script (see **Appendix G**), the RA will contact these Veterans by phone up to three weeks following the opt-out card mailing (making up to 5 attempts if they cannot reach the Veteran) to: 1) describe the study, 2) request participation, including potential randomization to one of three study arms if deemed eligible following the initial index screen, participation in subsequent surveys, and possible contact by phone to invite participation in a qualitative interview; and 3) obtain verbal consent. The RA will review the elements of informed consent and answer any questions the potential respondent might have. Among Veterans who verbally consent to participate, the RA will administer the index unmet need screen and, if Veteran is eligible for the RCT (i.e., 1 or more unmet needs) randomize them to one of the three trial arms using the sealed opaque envelope program (see **Appendix A** for details).

Step 4 (recruitment for qualitative interviews; Veterans): Among study participants, we will purposefully sample 60 Veterans to participate in qualitative interviews. Sample selection and recruitment will be conducted on a rolling basis after the 6-month unmet needs re-screen is completed. The study RA will phone selected Veterans, ask for participation in an interview, and among those who accept, schedule an interview time. Note: As part of the RCT informed consent process, participants will be told that they may be contacted by phone to participate in a qualitative interview, which we believe eliminates the need to mail opt-out cards prior to contacting Veterans by phone for this phase of the study. During this initial call we will not re-consent participants but will review and remind potential participants of the purpose of the interviews and the elements of informed consent.

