Appendix A: Description of the Intervention and Randomization

Unmet Needs Screen:

Veterans (anticipated N=1760) will be screened for unmet needs (index screen) and those identified as having at least one unmet need (target N=880) will be randomized to one of three study arms and screened again 6-months later. We will use the sealed opaque envelope program to generate randomization. For the index screen, a study Research Assistant (RA) will administer the screening instrument to Veterans by phone prior to the Veteran's upcoming primary care (PC) clinic appointment to gather data on nine unmet needs (full screen in **Appendix I**). Six months after the index screen, the RA will re-screen each Veteran participant by phone. For each completed screen, we will provide Veterans \$15 for their time.

After the RA determines each participant is eligible (see Section 5.2. Recruitment Methods), randomization will occur by the RA opening sealed envelopes that reveal the treatment assignments (screening, awareness, or assistance). Envelopes will be opened for each participant in the order they are recruited. The RA will then inform the participant of their assignment.

Resource Sheets:

For Veterans in the Awareness and Assistance arms, the RA will provide (via U.S mail) Resource Sheets tailored to the unmet needs identified in the index screen. During the index screen (by phone), the RA will inform the Veteran that they will receive a Resource Sheet in the mail and mail the Resource Sheets to the Veteran within two days of the index screen. During the index screen, the RA will additionally ask the Veteran if they would also like to receive the Resource Sheets via email. For Veterans who respond affirmatively, the RA will send the Resource Sheets as an email attachment during the index screen phone call and offer to review its content with them. The email message will be sent via encrypted email and will not solicit reply. (**Appendix G** contains the phone script for this interaction, and **Appendix P** contains the Resource Sheet email text and the cover letter for mailing.)

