i. Within the past 6 months, you worried that your food would run out before you got money to buy more.

- Often true
- Sometimes true

- Never true

ii. Within the past 6 months, the food you bought just didn't last and you didn't have money to get more.

- Often true
- Sometimes true
- Never true

10a. (If Often/Sometimes true to 10i or 10ii): Are you already receiving assistance with your food needs?

10b. (If Yes to 10a): Would you like additional assistance?

10c. (If No to 10a): Would you like assistance with your food needs?

LEGAL AND TRANSPORTATION

11. Are you currently dealing with any legal issues, for which you may need assistance?

- Yes
- No

11a. (If Yes): Are you already receiving assistance with your legal needs?

11b. (If Yes to 11a): Would you like additional assistance?

11c. (If No to 11a): Would you like assistance with your legal needs?

12. In the past 6 months, has lack of transportation kept you from medical appointments, meetings, work, or getting things needed for daily living: *Check all that apply*

- Yes, it has kept me from medical appointments or from getting my medications
- Yes, it has kept me from non-medical meetings, appointments, or getting the things that I need
- No

12a. (If Yes): Are you already receiving assistance with your transportation needs?

12b. (If Yes to 12a): Would you like additional assistance?

12c. (If No to 12a): Would you like assistance with your transportation needs?

SOCIAL AND EMOTIONAL STATUS

13. In the last 6 months, how often did you feel lonely or isolated?

- Never
- Rarely
- Sometimes
- Often

- Always

13a. (If Sometimes/Often/Always): Are you already receiving assistance with your feelings of loneliness or isolation?

13b. (If Yes to 13a): Would you like additional assistance?

13c. (If No to 13a): Would you like assistance with your feelings of loneliness or isolation?

14. Stress is when someone feels tense, nervous, anxious, or can't sleep at night because their mind is troubled. In the last 6 months, how often did you feel stressed?

- Not at all
- A little bit
- Somewhat
- Quite a bit
- Very much

14a. (If Somewhat/Quite a bit/Very much): Are you already receiving assistance with your feelings of stress?

14b. (If Yes to 14a): Would you like additional assistance?

14c. (If No to 14a): Would you like assistance with your feelings of stress?

EXPOSURE TO VIOLENCE

15. Is anyone in your life hurting or threatening you?

- Yes
- No

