Appendix P. Mail and Email Text for Delivering Resource Sheets to Veterans

1. Cover Letter to Veterans mailed with Resource Sheets:

Veterans' Resource Needs Study

(Address of Site location)

(Phone number for Site RA)

(Date)

Hello, and thank you for participating in our study!

When we spoke on the phone several days ago, I promised to mail you some written material on agencies and programs that may be able to help you with the needs that you identified.

Please read through the enclosed material, and contact any of the listed programs or services directly at any time.

If you have questions about enclosed material, please call me at the number above.

Thank you.

2. Email message to Veterans who choose to have Resource Sheet emailed:

Hello, and thank you for participating in our study!

The written material about Veterans' resources that I mentioned on the phone today is attached to this message for you to download and open. You will also receive a printed copy in the mail in a few days.

Thank you.

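### For a Veteran who reports being hurt or threatened, the scripts shown announce the posting of tailored Resource Sheets without asking which delivery route is safe

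*Combined protocol and SAP*

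**What the plan says.** Section 3.0 lists safety among the nine unmet needs ("transportation, legal needs, employment, safety, social isolation, stress"). In Appendix I the exposure-to-violence item, number 15, is "Is anyone in your life hurting or threatening you", answered Yes or No. Section 5.2, Step 3, sets the entry rule: "if Veteran is eligible for the RCT (i.e., 1 or more unmet needs) randomize them to one of the three trial arms".

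Under Resource Sheets, Appendix A has the research assistant send, by US mail, "Resource Sheets tailored to the unmet needs identified in the index screen" to participants in the Awareness and Assistance arms. It describes a sheet for each of the nine needs and makes no exception for safety. Appendix G, items 10 (Awareness) and 11 (Assistance), both say "I will mail you this material within the next two business days". The participant is then asked only whether they would also like the material by email. The email text in Appendix P tells the recipient that a paper copy will follow. The posted cover letter in the same appendix refers to agencies that may "help you with the needs that you identified".

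On risk, section 5.1 states: "Potential risks are minimal and would primarily involve loss of confidentiality".

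**The concern.** The study itself asks for the disclosure and then, by default, posts material that depends on the answer. For most needs, such as transport or employment, a sheet seen by someone else at home is at worst an embarrassment. For the safety item, the person who opens or notices the envelope may be the person the Veteran reported. An envelope cannot be recalled once it has been sent.

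The plan treats confidentiality as its main risk, but the risk and protection text does not consider a household member seeing mailed study material. What is at stake is participant safety and confidentiality. No estimate, test or error rate in the plan depends on it.

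**Working it through.** The plan gives no figure to reproduce here. The check follows one participant through the text and then sizes the group.

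**Path**

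1. *Eligibility.* Safety is one of the nine needs (section 3.0), and item 15 is the only item in Appendix I that addresses it. One need suffices (section 5.2, Step 3; Appendix G, item 8). A Yes to item 15 can therefore qualify a Veteran by itself, in which case the safety sheet could be the only sheet in the envelope.
2. *Mailing.* Appendix A applies postal delivery to both referral arms, with a sheet for every need. Items 10 and 11 announce the mailing as settled. In the Assistance arm the script allows the social worker's help to be declined, but it offers no such choice about the posted sheets.
3. *Email.* Email adds to post and does not replace it (Appendix A; Appendix P email text). A Veteran who chooses email still gets paper.
4. *Preference questions.* Items 15b and 15c ask whether help is wanted, but nothing shown makes the mailing depend on the answer. Item 15a is also triggered by frequency answers (Sometimes, Often, Always) that item 15, a Yes/No question, does not offer. Read literally, 15a to 15c may never be asked.
5. *Address check.* Items 9, 10a and 11b verify the mailing address in connection with the gift card. This confirms that the address is correct, not that it is safe.
6. *Household information.* Appendix I, item 1, records whether a spouse, partner or other adults live with the Veteran. No rule shown uses it for mailing.
7. *General protections.* The protection text in section 5.1 covers data security, distress, crisis-line hand-off, an on-call research social worker, and advice to contact the primary care team when unforeseen risks to health or welfare appear. The last two could well be used after a Yes to item 15. Neither governs what is posted.

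**Size**

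- Randomised: 880 in three equal arms (section 5.6).
- Mailed arms: 880 × 2/3 = 586.7, about 587 (2 × 293 = 586 from the stated arm size).
- Share answering Yes to item 15: not given in the documents. Assumed range 1% to 5%.
- 587 × 0.01 = 5.9, about 6. 587 × 0.05 = 29.4, about 29.

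These are upper bounds under the assumed prevalence. Item 15 asks about anyone in the Veteran's life, so it includes people who do not share the address. Exposure further requires that the other person sees the post and that the sheet can be recognised as concerning safety.

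**The case against.** The strongest reply is that the exposure depends on material not seen here. The cover letter names no need and by itself reveals nothing about violence. Whether a safety sheet reveals anything depends on its title and wording, and the sample sheets of Appendix O were not in the text available to this review. The earlier items of the Appendix G script were not available either, and they might contain a safe-contact question. This stands, and it limits the point to what could happen under the text shown. It does not remove the point, because the script after randomisation, the mailing rule in Appendix A and both Appendix P texts are available, and none of them refers to a delivery preference.

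A reader might infer that participants have no way to decline or redirect the post. The documents do not support that. The research assistant invites questions and checks the address on the same call, and section 5.7 allows withdrawal at any time. The supportable statement is that the shown script does not prompt for a safe route.

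A reader might also infer that the plan breaches its own commitment to monitor privacy. The Safety and Data Monitoring Plan commits to monitoring recruitment, survey collection and interviews. Mailing of Resource Sheets is not on that list, so there is no direct contradiction.

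Finally, one might argue that harm or withdrawal would differ between arms and bias the comparison. Nothing in the documents shows that at most 6 to 29 people among about 587 would shift either measurably. That argument is speculative and carries no weight here.

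**Conclusion.** The point holds as a participant-safety gap in the delivery procedure. In the text shown, a Veteran who answers Yes to item 15 and is allocated to Awareness or Assistance is sent tailored sheets by post, by default and without being asked whether post is safe. Any exposure would come from an identifiable safety sheet reaching a shared address, not from the letter alone.

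At most about 6 to 29 Veterans would be affected, assuming that 1% to 5% answer Yes and that recruitment reaches 880 in equal arms. The number actually exposed would be no larger and may be much smaller. Confidence is moderate, because the sample sheets and the earlier script items could contain a safeguard. The change is still worth making: the possible harm is serious and irreversible, and the remedy is small.

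**What to change.** In Appendix A and in Appendix G, items 10 and 11, add a step that applies when item 15 is Yes. Before ending the call, the research assistant asks by which route the Veteran wants the safety sheet: post, email only, or reviewed by phone. The research assistant follows that choice, leaves the safety sheet out of the envelope if post is declined, and records the route in REDCap. The sentence announcing the mailing, and the promise of a paper copy in the Appendix P email, then need a conditional version so that they agree with the choice. If an earlier script item already asks about safe contact, a cross-reference to it from items 10 and 11 would do instead.

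The cost is a short script addition, one data field and an IRB amendment. The downside is a small loss of uniformity, since a few participants in the referral arms would get the safety information by a different route. Allocation, outcomes and sample size are unchanged.

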Appendix I: Index Unmet Needs Screening Tool

DEMOGRAPHICS

1. Please indicate which of following types of people currently live with you in your household (*check all that apply*)

- My spouse or partner
- My child(ren) under age 18
- My adult child(ren) age 18 or older
- My parent(s)
- Extended family
- Roommate(s) not related to me
- Other individuals

2. Overall, which one of the following best describes how well you are managing financially these days?

- Living comfortably
- Doing OK
- Just getting by
- Finding it difficult to get by

3. Are you of Hispanic or Latino origin or descent?

- Yes, Hispanic or Latino
- No, not Hispanic or Latino

4. What is your race? Please select all that apply.

- White
- Black or African-American
- Asian
- Native Hawaiian or other Pacific Islander
- American Indian or Alaska Native
- Other

5. What is your gender

- Man
- Woman
- Transgender man
- Transgender woman
- Non-binary
- Other

HOUSING AND UTILITIES

6. In the past 6 months, have you been living in stable housing that you own, rent, or stay in as part of a household?

- Yes
- No

7. Are you worried or concerned that in the next 2 months you may NOT have stable housing that you own, rent, or stay in as part of a household?

- Yes
- No

7a. (If Yes to Q6 or Q7): Are you already receiving assistance with your housing needs?

7b. (If Yes to 7a): Would you like additional assistance?

7c. (If No to 7a): Would you like assistance with your housing needs?

8. In the past 6 months has the electric, gas, oil or water company threatened to shut off service in your home?

- Yes
- No
- Already shut off
- Not applicable

8a. (If Yes/Already shut off): Are you already receiving assistance with your gas, oil or water company needs?

8b. (If Yes to 8a): Would you like additional assistance?

8c. (If No to 8a): Would you like assistance with your gas, oil or water company needs?

EMPLOYMENT AND FOOD

9. Are you currently:

- Employed for wages
- Self-employed
- Out of work for 1 year or more
- Out of work for less than 1 year
- A Homemaker
- A Student
- Retired
- Unable to work

9a. Do you want help finding or keeping work or a job (check all that apply)?

- Yes, help finding a job
- Yes, help keeping work
- I do not want or need help
- I am already receiving assistance with my employment needs

10. How often were the following statements true for you in the past 6 months?

i. Within the past 6 months, you worried that your food would run out before you got money to buy more.

- Often true
- Sometimes true

- Never true

ii. Within the past 6 months, the food you bought just didn't last and you didn't have money to get more.

- Often true
- Sometimes true
- Never true

10a. (If Often/Sometimes true to 10i or 10ii): Are you already receiving assistance with your food needs?

10b. (If Yes to 10a): Would you like additional assistance?

10c. (If No to 10a): Would you like assistance with your food needs?

LEGAL AND TRANSPORTATION

11. Are you currently dealing with any legal issues, for which you may need assistance?

- Yes
- No

11a. (If Yes): Are you already receiving assistance with your legal needs?

11b. (If Yes to 11a): Would you like additional assistance?

11c. (If No to 11a): Would you like assistance with your legal needs?

12. In the past 6 months, has lack of transportation kept you from medical appointments, meetings, work, or getting things needed for daily living: *Check all that apply*

- Yes, it has kept me from medical appointments or from getting my medications
- Yes, it has kept me from non-medical meetings, appointments, or getting the things that I need
- No

12a. (If Yes): Are you already receiving assistance with your transportation needs?

12b. (If Yes to 12a): Would you like additional assistance?

12c. (If No to 12a): Would you like assistance with your transportation needs?

SOCIAL AND EMOTIONAL STATUS

13. In the last 6 months, how often did you feel lonely or isolated?

- Never
- Rarely
- Sometimes
- Often

- Always

13a. (If Sometimes/Often/Always): Are you already receiving assistance with your feelings of loneliness or isolation?

13b. (If Yes to 13a): Would you like additional assistance?

13c. (If No to 13a): Would you like assistance with your feelings of loneliness or isolation?

14. Stress is when someone feels tense, nervous, anxious, or can't sleep at night because their mind is troubled. In the last 6 months, how often did you feel stressed?

- Not at all
- A little bit
- Somewhat
- Quite a bit
- Very much

14a. (If Somewhat/Quite a bit/Very much): Are you already receiving assistance with your feelings of stress?

14b. (If Yes to 14a): Would you like additional assistance?

14c. (If No to 14a): Would you like assistance with your feelings of stress?

EXPOSURE TO VIOLENCE

15. Is anyone in your life hurting or threatening you?

- Yes
- No

15a. (If Sometimes/Often/Always): Are you already receiving assistance with your being hurt or threatened?

15b. (If Yes to 15a): Would you like additional assistance?

15c. (If No to 15a): Would you like assistance with your being hurt or threatened?

